**RUN;**

Results of the MMRM (N, mean, SE and 95% CI per dose group and timepoint) will be presented in tables and displayed graphically.

#### MCPMod Analysis

The adjusted mean estimates of the change from baseline at Week 10 for each dose and their estimated variance-covariance matrix from the MMRM model are used in the trial analysis stage. Then, the multiple pair-wise comparison procedure will be implemented using the optimal contrast tests which control the family-wise type I error rate at one-sided  $\alpha = 0.10$ .

For the MCPMod test, the optimal contrasts corresponding to the candidate models are calculated as in the trial design stage (using the R-function optContr using weights proportional to the sample size of each dose group) and are shown in [Table 7.4.1: 1](#) below. These contrasts will be updated using the expected model means from the candidate set and the estimated variance-covariance matrix from the data. The final contrasts will be presented in the CTR.

Table 7.4.1:1 Optimal contrast coefficients

| Model              | Optimal Contrast Coefficients for Dose |        |        |        |       |
|--------------------|--|--------|--------|--------|-------|
|                    | 0                                      | 5mg    | 25mg   | 75mg   | 125mg |
| Linear             | -0.583                                 | -0.209 | -0.110 | 0.136  | 0.765 |
| E max 1 | -0.736                                 | -0.175 | 0.064  | 0.243  | 0.604 |
| E max 2 | -0.862                                 | 0.052  | 0.177  | 0.206  | 0.425 |
| Sigmax             | -0.684                                 | -0.250 | 0.032  | 0.276  | 0.627 |
| Exponential        | -0.479                                 | -0.187 | -0.161 | -0.016 | 0.842 |

Proof of concept is established if at least one dose-response model is statistically significant, i.e., the null hypothesis of a flat dose-response curve is rejected indicating a benefit of one BI 1358894 dose over placebo.

Once the significance of a dose-response signal is established, the dose-response profile and the target dose can be estimated using the model averaging method.

The selected dose-response model(s) is re-fitted to the data without any parameter assumptions to generate a set of new estimates of the model parameters from the data. The final dose-response model is obtained via the weighted model averaging of the significant models (p-value<0.10) based on Akaike Information Criterion (AIC) (the smaller the AIC value the better the model fit). The weights for each significant model ( $M_k$ ) are given by,

$$w(M_k) = \frac{\exp(-0.5 * AIC(M_k))}{\sum_{i=1}^K \exp(-0.5 * AIC(M_i))}$$

where  $AIC(M_k)$  is the AIC for model  $M_k$ .

The estimate of the target dose is the smallest dose producing an effect greater than or equal to the target effect size of 0.32 based on the final dose-response model (accounting for safety and other relevant information). Specifically, the target effect size considers the observed standard deviation (SD) and the adjusted mean treatment effect. Thus, if the observed SD is 9.5, then to achieve the target effect size of 0.32, the observed placebo-adjusted difference would need to be at least 3. Test statistics and p-values will also be displayed for different dose-response models. Figures and tables will be displayed for the MCPMod modelling.

The following displays are planned:

- Table of the contrast coefficients per dose group and candidate model, together with the MCPMod test statistics and p-values for each model and the critical value
- For the average model, figure of the dose-response curve
- For all significant model shapes, figures of the dose-response curve plus 95% confidence band (of the predicted shape)

The MCPMod trial analysis will be implemented by calling an R function/package within SAS. Please see [Section 10.3](#) for R code to implement the MCPMod analysis.

#### 7.4.2 Sensitivity analysis, supplementary analysis, subgroup analysis, exploratory analysis of the primary endpoint(s)

##### 7.4.2.1 Sensitivity analyses

To explore the robustness of inferences (results) from the main estimator to deviations from its underlying assumptions, several sensitivity analyses will be conducted targeting the same estimand, the hypothetical estimand. In the sensitivity analyses that follow, a certain aspect of the main analysis of the primary endpoint is altered to allow the possibility of identifying which assumptions, if any, are responsible for potential differences observed.

##### Exclude virtual collections of ZAN-BPD

The first sensitivity analyses to the primary analysis of the primary endpoint will assess the assumption of no discernible difference between the in-person and virtual collection of the ZAN-BPD. Unlike the primary analysis, this sensitivity analysis will assume a difference between the in-person and virtual data assessments and shall exclude all virtual collections of

the ZAN-BPD. This analysis of the primary endpoint will use the hypothetical estimand (the same estimand as that of the primary analysis). However, here we recognize the virtual collection as a deviation. This sensitivity analysis will follow the same analysis methodology (MCPMod/MMRM) as specified in the primary analysis, but with the exclusion of all virtual collections of the ZAN-BPD.

Dose response patterns

If considered necessary and for the purpose of further model refinement, the MCPMod analysis may be repeated on the primary endpoint but with an extended set of dose response patterns, including the original candidates.

Additional risk factors

Further sensitivity analyses to the primary analysis of the primary endpoint will be conducted with additional covariates of interest. The additional fixed categorical covariates of stable concomitant psychotherapy use (Yes, No) and Sex (Male, Female) will be included into the MMRM model.

PPS

Sensitivity analysis of the primary and secondary efficacy endpoints using the PPS may be conducted if more than 10% of patients in FAS have an iPD which lead to exclusion from the PPS.

7.4.2.2 Supplementary analyses to the primary endpoint

Supplementary analysis is a general description for analyses that are conducted in addition to the main and sensitivity analysis to provide additional insights into the understanding of the treatment effect. Supplementary analyses should generally be given lower priority than sensitivity analyses. Please see below [Table 7.4.2.2:1](#) for an overview of the supportive sensitivity and supplementary analyses to the main analysis of the primary endpoint.

Table 7.4.2.2: 1 Overview of the main analysis of the primary endpoint and its sensitivity/supplementary analyses.

| Primary Analysis               | Sensitivity Analysis | Supplementary Analysis 1             | Supplementary Analysis 2                 |
|---------------------------------------|-----------------------------|---|---|
| Hypothetical estimand (main analysis) | Hypothetical estimand       | Treatment policy (repeats primary analysis) | Treatment policy (repeats sensitivity analysis) |

|  |  |   |  |
|--|--|---|--|
| Does not recognize alternate collection of the ZAN-BPD.                  | Recognizes alternate collection of the ZAN-BPD.  | Does not recognize alternate collection of the ZAN-BPD.                       | Recognizes alternate collection of the ZAN-BPD.  |
| Assumes no discernible difference between in-person and virtual ZAN-BPD. | Assumes a difference between the in-person and virtual assessment.

Excludes virtual collections of ZAN-BPD. | Assumes no discernible difference between in-person and virtual data ZAN-BPD. | Assumes a difference between the in-person and virtual assessment.

Excludes virtual collections of ZAN-BPD. |

### Treatment policy estimand

1. Supplementary analysis 1 repeats *the primary analysis of the primary endpoint* but under the treatment policy estimand i.e., effectiveness/intention to treat. Under treatment policy, we assess the treatment effect irrespective of intercurrent events, hence all measurements are relevant. We maintain the assumption of no discernible difference between the in-person and virtual collection of the ZAN-BPD. The treatment policy estimand will use all available ZAN-BPD data including data collected after treatment discontinuation or other intercurrent events. If telemedicine assessments need to be implemented due to COVID-19 related factors, the treatment policy estimand will use all available data regardless of administration method (i.e., in-person, video, and audio). This supplementary analysis to the primary endpoint will follow the same analysis methodology (MCPMod/MMRM) as specified in the primary analysis.
2. Supplementary analysis 2 repeats the *sensitivity analysis of the primary endpoint* (exclude virtual collections of ZAN-BPD) but under the treatment policy estimand i.e., effectiveness/intention to treat. Here, and like the sensitivity analysis, we maintain the assumption of a discernible difference between the in-person and virtual collection of the ZAN-BPD and shall exclude all virtual collections of the ZAN-BPD. The treatment policy estimand will use all other available ZAN-BPD data including data collected after treatment discontinuation or other intercurrent events. This analysis to the primary endpoint will follow the same analysis methodology (MCPMod/MMRM) as specified in the primary analysis.

### 7.4.2.3 Subgroup analyses to the primary endpoint

The primary efficacy endpoint will be further analyzed for the AiCure adherent subgroup as defined in [Section 6.3](#) and [6.4](#). This study is not adequately powered to confirm treatment differences in any subgroup analysis. Any subgroup analyses performed will be considered exploratory. This subgroup analysis will explore if the treatment effect differs in the AiCure adherent subgroup. The 3 subgroups are: (1) overall adherence  $\geq 60\%$ , (2) overall adherence  $\geq 75\%$ , and (3) overall adherence  $\geq 90\%$ . The conduct of these analyses is subject to the available sample size of the subgroup and more categories could be defined. The same statistical approach and methods used for the primary analysis of the primary efficacy endpoint will be used.

#### Subgroup analysis by Region and Race

The least square mean estimates from the MMRM model (as done for the primary endpoint) on the change from baseline in ZAN-BPD at Week 10 for each dose group will be compared against several subgroups of interest, particularly regions and race. For the subgroups on regions please see [Table 10.2:1](#). For the subgroups on race, they are: white and non-white. The analyses of the subgroups will follow the same methods as detailed for the primary analysis of the primary endpoint.

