## **5.7 APPROPRIATENESS OF MEASUREMENTS**

All measurements performed during this trial are standard measurements and will be performed in order to monitor safety aspects or assess treatment response in an appropriate way. Therefore, the appropriateness of all measurements applied in this trial is given.

Information about race should be obtained from all study participants as allowed by local regulations. It is necessary to collect these data to assess consistency of treatment effects across different patient populations.

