#### 7.5 DETERMINATION OF SAMPLE SIZE

Sample size is estimated assuming a maximum standardized effect size of 0.32, which is based on a mean difference between placebo and BI 1358894 of 3.0 and standard deviation of 9.5 for the primary endpoint, a one-sided alpha of 0.10, a treatment allocation ratio of 2.5:1:1:1:2 (placebo, BI 5mg, BI 25mg, BI 75mg, BI 125mg, respectively) and the pre-specified models listed in section [7.2.2.1](#). Information on the change from baseline and its standard deviation is limited since there is no BoPD approved drug. BoPD is a symptomatic and clinically heterogeneous condition and in clinical studies a high discontinuation rate has been observed. Consequently, sample size assumptions are based on expert opinion, previous BoPD research and a quetiapine pivotal trial ([R19-1108](#), [R19-1645](#), [P11-04859](#)).

For the PoC analysis of the BI 1358894 dose groups and placebo using MCPMod approach with the parameters as listed in section [7.2.2](#), a sample size of 285 (95:38:38:38:76) evaluable patients are needed to establish PoC with about 81% average power (one-sided 10% alpha level). The powers for each model shape under different assumptions are summarized in the table below.

Assuming a 20% dropout rate is considered reasonable based on unique characteristics of this population. Therefore, a total sample size of approximately 355 randomized patients are needed for this phase II trial:

- 119 patients in placebo arm
- 47 patients in each of the three lowest BI 1358894 arms
- 95 patients in the highest BI 1358894 arm

The calculations for the PoC step have been performed using DoseFinding R-package ([R15-2001](#)). The R codes for the sample size calculations as well as the analyses using the MCPMod approach will be provided in the TSAP. The family-wise type I error rate at one sided  $\alpha = 10\%$  is controlled in the sample size calculations and the analyses.

Table 7.5: 1 Power of MCPMod for each candidate set model and average power for change from baseline in ZAN-BPD at Week 10

Model	Assumption A	Assumption B	Assumption C
Maximum effect size	0.32 (Mean=3, SD=9.5)	0.35 (Mean=3.3, SD=9.5)	0.38 (Mean=3.6, SD=9.5)
Linear	81.9%	86.7%	91.6%
E max 1	81.7%	87.7%	91.6%
E max 2	75.2%	82.7%	86.6%
Sigmax	85.4%	89.1%	93.7%
Exponential	81.0%	85.8%	90.5%
Average	81.1%	86.4%	90.8%

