#### MMRM analysis

The change from baseline in ZAN-BPD at Week 10 for each dose group as well as the corresponding variance-covariance matrix are estimated by a mixed effects model repeated measure (MMRM) including the fixed categorical covariates of treatment, visit and the baseline ZAN-BPD total score strata indicator ( $\leq 18$  vs.  $\geq 19$ ), the continuous fixed covariate of baseline ZAN-BPD total score, and treatment-by-visit interaction, as well as baseline-by-visit interaction. Patient is considered as random. The unstructured covariance matrix is used to estimate the within subject variability. The Kenward-Roger approximation will be used to estimate the denominator degrees of freedom. Analyses will be implemented using SAS 9.4 PROC MIXED.

More specifically, the change in ZAN-BPD from baseline (Visit 2), at Visits 3, 4, 5, 6, 7 and 8 (Weeks 1, 2, 4, 6, 8 and 10) will be evaluated using an MMRM accounting for the following sources of variation: 'treatment', 'visit', 'baseline ZAN-BPD strata indicator' ( $\leq 18$  vs.  $\geq 19$ ),

‘baseline ZAN-BPD’ as a continuous covariate, and the ‘treatment\*visit’ and ‘baseline\*visit’ interaction as fixed effects, as well as the random ‘subject’ effect. The methods described in [Section 10.1](#) will be utilized to resolve model non-convergence.

SAS code for MMRM:

The following SAS code will be used to calculate the MMRM.

```
PROC MIXED DATA=indata cl method=reml;
    CLASS visit trt stratum subject;
    MODEL ept = stratum visit*trt base*visit / ddfm=kr s CL;
    REPEATED visit / subject= subject type=un r rcorr;
    LSMEANS visit*trt / pdiff=all om cl alpha=0.10 slice=visit;
```

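### For region and race, the visible SAP plans no estimate of how the drug effect differs between subgroups, so separate subgroup results cannot be read as evidence on consistency

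*SAP*

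**What the plan says.** SAP 7.4.2.3, under the heading on region and race, takes the Week 10 least-squares means from the MMRM and says that these "for each dose group will be compared against several subgroups of interest, particularly regions and race". Race is split into white and non-white; the regions are listed in Table 10.2:1. On method it adds: "The analyses of the subgroups will follow the same methods as detailed for the primary analysis of the primary endpoint".

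The primary method is in SAP 7.4.1. The MMRM statement is "MODEL ept = stratum visit*trt base*visit / ddfm=kr s CL", which holds the baseline stratum, treatment by visit and baseline by visit. The adjusted means then go into MCPMod, which ends in a yes/no proof-of-concept verdict. SAP 6.5 says that centre and country are not in the model and refers to Section 6.4 for the effect of region.

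The opening of SAP 7.4.2.3 says that the study is not powered to confirm subgroup differences and that subgroup analyses are exploratory. For Asian participants, about 4% of the sample, the SAP plans descriptive statistics only.

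Protocol 5.7 gives this reason for recording race: "It is necessary to collect these data to assess consistency of treatment effects across different patient populations".

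**The concern.** Consistency of a treatment effect is a statement about the difference between subgroups in that effect. A model with no treatment-by-subgroup term, fitted separately in each subgroup, does not report that difference. The reader is left to set one group's means, and possibly its verdict, beside another's, when the groups may differ greatly in size. A significant result in the large group and a non-significant one in the small group is then easily taken as a difference in drug effect when it may only reflect numbers.

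Small groups also make the separate fits fragile. Six post-baseline visits need 6 x 7 / 2 = 21 covariance parameters, and five arms by six visits need 30 means. In a subgroup holding 20% of the evaluable patients, the 5, 25 and 75 mg arms would have about 38 x 0.2 = 7.6 patients each.

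What is at stake is interpretation. A Phase II report could suggest a regional or racial inconsistency that is not there, or leave a real one without an estimate.

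**Working it through.** **Inputs.** From Protocol 7.5: a "one-sided alpha of 0.10", a "mean difference between placebo and BI 1358894 of 3.0 and standard deviation of 9.5 for the primary endpoint", "a treatment allocation ratio of 2.5:1:1:1:2", and "a sample size of 285 (95:38:38:38:76) evaluable patients are needed to establish PoC with about 81% average power". The five candidate shapes are those of Protocol Table 7.2.2.1:1. The white/non-white split and the regions are not visible, so the split is assumed and varied. Each subgroup is assumed to keep the planned allocation. The calculation treats the Week 10 value as a single measurement with SD 9.5 and df = N - 5; it does not simulate the full MMRM.

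**Step 1: reproduce the plan.** The optimal contrast for a shape with means mu_i is c_i proportional to n_i x (mu_i - weighted mean), scaled to unit length. For the Linear shape the weighted mean dose is (38x5 + 38x25 + 38x75 + 76x125)/285 = 13490/285 = 47.33. The unscaled coefficients are 95x(-47.33), 38x(-42.33), 38x(-22.33), 38x27.67 and 76x77.67. Scaled, they are -0.583, -0.209, -0.110, 0.136 and 0.765, as in SAP Table 7.4.1:1. All 25 coefficients in that table reproduce to three decimals. Proof of concept is declared when the largest of the five contrast t-statistics exceeds the multivariate-t critical value (about 1.61 for the full sample). Simulated average power at 3.0 points is 81.3%, against 81.1% in Protocol Table 7.5:1. Two single-shape entries do not reproduce (Emax2 81.9% against 75.2% stated; Exponential 78.8% against 81.0%), which does not affect this point.

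**Step 2: two subgroups, one identical effect.** With power p1 and p2 in two independent groups, the chance that exactly one shows proof of concept is p1(1 - p2) + p2(1 - p1). Powers are averaged over the five shapes, with 285 evaluable:

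| Assumed split | p1 | p2 | Exactly one positive |
|---|---|---|---|
| 50:50 | 60% | 59% | 48% |
| 60:40 | 65% | 53% | 49% |
| 70:30 | 70% | 45% | 52% |
| 80:20 | 74% | 37% | 56% |
| 90:10 | 78% | 26% | 63% |

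For example, at 80:20: 0.74 x 0.63 + 0.37 x 0.26 = 0.466 + 0.096 = 0.56.

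**Step 3: how far this depends on the assumptions.** With no drug effect it is 2 x 0.10 x 0.90 = 18%. Over splits of 50:50 to 80:20 it is 42-43% at a true effect of 1.5 points, 48-50% at 2 points, 41-54% at 3.6 points and 26-45% at 4.5 points. With 355 analysed instead of 285 it is 45-55%. For regions it is a per-pair figure: 50% for a pair among three equal regions, 48% among four and 47% among five. The chance that three equal regions do not all agree is 75%.

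**Step 4: the direct estimate.** For 125 mg against placebo, the full-sample SE is 9.5 x sqrt(1/95 + 1/76) = 1.462. With a fraction f in one group, the SE of the between-group difference is 1.462 x sqrt(1/f + 1/(1 - f)):

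- 50:50: 1.462 x 2.000 = 2.9; 90% half-width 1.645 x 2.92 = 4.8
- 70:30: 1.462 x 2.182 = 3.2; half-width 5.2
- 80:20: 1.462 x 2.500 = 3.7; half-width 6.0

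An interaction test at two-sided 10% (level assumed) declares a false difference in 10% of trials; simulating a 4-df version gave 9.9-10.0%. Its power for a true 3-point difference between groups is about 27% at 50:50 and 21% at 80:20.

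**The case against.** The case on the other side has five parts.

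- **Hidden text.** SAP 6.5 sends the reader to Section 6.4 for region, and neither that section nor Table 10.2:1 can be seen. A reader might infer that no between-subgroup estimate is planned anywhere. The documents do not support that; one can say only that none appears in the visible text. This stands.
- **No named MCPMod test.** The region and race paragraph names only MMRM least-squares means, whereas the supplementary analyses in SAP 7.4.2.2 name MCPMod and MMRM together. A reader might infer that a proof-of-concept verdict is certain to be issued in every subgroup. The same-methods sentence allows that reading but does not require it. If MCPMod is not run by subgroup, the figures in Step 2 do not apply, although the between-subgroup difference is still not reported.
- **The outputs suffice.** The SAP tabulates means and SEs, and its code requests pairwise differences. With separate fits, a reader could subtract one subgroup's effect from another's and combine the SEs. This is correct, so the gap is in what the plan undertakes to report. It remains a gap, because the derived quantity is the one that bears on consistency.
- **The SAP already limits inference.** It calls the subgroups exploratory and underpowered, and no visible text treats discordant verdicts as inconsistency or ties a Phase III decision to them. This stands and lowers the severity. It does not supply the missing estimate. Setting 48-56% beside a test's 10% error rate also compares a pattern that nobody has undertaken to declare with a formal decision.
- **The remedy is weak.** A pooled model still fits 30 arm-by-visit means per subgroup and shares only the covariance, and its power is low. This is true and is stated as the cost under the fix.

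**Conclusion.** The point holds as a limited one. The primary MMRM, as reused for region and race, has no subgroup or treatment-by-subgroup term, and the visible text plans no estimate or interval for the quantity that measures consistency.

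If the MCPMod test is repeated in each subgroup, disagreement between verdicts is weak evidence of anything. It would occur in about 48-56% of trials with an identical effect in both groups, given the planning effect, 285 evaluable and an assumed split between 50:50 and 80:20. A reader might take about half as a general rate. It is not: the figure moves with the true effect and the split, and with more than two regions it applies to each pair.

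A reader might also infer a threat to the primary conclusion. There is none: the primary test and its type I error are unaffected. This is an optional, low-severity improvement to an exploratory analysis.

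**What to change.** For region and for race, fit one MMRM on the FAS with the primary terms plus subgroup, subgroup*visit and treatment*visit*subgroup, keeping a common unstructured covariance. Report the Week 10 difference between subgroups in the placebo-adjusted effect, at least for 125 mg, with a two-sided 90% interval, beside the subgroup least-squares means. If any MCPMod result is shown by subgroup, label it descriptive and state that it is not used to judge consistency. If Section 6.4 already specifies such an estimate, a cross-reference in 7.4.2.3 is enough.

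The cost is a few lines of SAS and one table or forest plot, with no change to the protocol or to data collection. The drawback is a wide interval: about plus or minus 4.8 points at 50:50 and 6.0 at 80:20, against a planned effect of 3.0. It can describe the uncertainty but cannot confirm consistency, and the text should say so.
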